7.4 Exploratory Biomarker Sampling

Blood (up to 48 mL) and urine (up to 20 mL) samples will be collected for exploratory biomarker analyses at timepoints specified in [Appendix A](#).

8 SAFETY ASSESSMENTS

Safety assessments will include AEs, clinical laboratory evaluations (including serum chemistry, hematology, endocrinology, and urinalysis), vital signs, physical examination, and 12-lead ECG.

8.1 Adverse Events

An AE is defined as any untoward medical occurrence in a patient administered a pharmaceutical product, which does not necessarily have a causal relationship with this treatment. An AE can therefore be any unfavorable and/or unintended sign (including a clinically significant abnormal laboratory finding), symptom, or disease temporally associated with the use of an IMP, whether or not related to the IMP. All AEs, including observed or volunteered problems, complaints, or symptoms, are to be recorded on the appropriate eCRF. The Investigator should update the appropriate eCRF if additional follow-up information becomes available (eg, the AE has subsided, stabilizes, or the condition becomes chronic in nature).

AEs, which include clinical laboratory test results, will be monitored and documented from the time of informed consent/assent until the end of the Follow-up Period (Study Visit 9). Patients should be instructed to report any event that they experience to the Investigator, whether or not they think the event is due to study drug. From the time of informed consent/assent, Investigators should make an assessment for AEs at each visit and record the event on the appropriate AE eCRF.

Wherever possible, a specific disease or syndrome rather than individual associated signs and symptoms should be identified by the Investigator and recorded on the eCRF. However, if an observed or reported sign or symptom is not considered a component of a specific disease or syndrome by the Investigator, it should be recorded as a separate AE on the eCRF. Additionally, the condition that led to a medical or surgical procedure (eg, surgery, endoscopy, tooth extraction, or transfusion) should be recorded as an AE, not the procedure itself.

Any medical condition already present at informed consent/assent should be recorded as medical history and not be reported as an AE unless the medical condition or signs or symptoms present at baseline change in severity, frequency, or seriousness at any time during the study. In this case, it should be reported as an AE.

Clinically significant abnormal laboratory or other examination (eg, ECG) findings that are detected during the study or are present at informed consent/assent and significantly worsen during the study should be reported as AEs. The Investigator will exercise his or her medical and scientific judgment in deciding whether an abnormal laboratory finding or other abnormal assessment is clinically significant. Thus, abnormal test results that are determined to be an error should not be reported as an AE, while laboratory abnormalities or other abnormal clinical findings (eg, ECG abnormalities) should usually be reported as an AE if any of the following are applicable:

- An intervention is required as a result of the abnormality;
- Action taken with the study drug is required as a result of the abnormality; or
- Based on the clinical judgment of the Investigator.

Clinically significant abnormal laboratory values occurring during the clinical study will be followed until repeat tests return to normal, stabilize, or are no longer clinically significant.

8.1.1 Adverse Reaction

All noxious and unintended responses to a medicinal product related to any dose should be considered an adverse reaction. “Responses” to a medicinal product means that a causal relationship between a medicinal product and an AE is at least a reasonable possibility, ie, the relationship cannot be ruled out.

8.1.2 Unexpected Adverse Reaction

An unexpected adverse reaction is defined as an adverse reaction, the nature or severity of which is not consistent with the applicable product information/reference safety information.

For setanaxib, the reference safety information is included in Section 5.3.7 of the IB currently in force. The reference safety information will be reviewed annually by the Sponsor and the periodicity of the review will be harmonized with the reporting period of the Development Safety Update Report, where possible.

8.1.3 Assessment of Adverse Events by the Investigator

The Investigator will assess the severity (intensity) of each AE and will also categorize each AE as to its potential relationship to the investigational study drug.

8.1.3.1 Assessment of severity

The severity of all AEs should be graded according to the CTCAE version 5.0. For those AE terms not listed in the CTCAE, the following grading system should be used:

- CTCAE Grade 1: Mild; asymptomatic or mild symptoms; clinical or diagnostic observations only; intervention not indicated;
- CTCAE Grade 2: Moderate; minimal local or noninvasive intervention indicated; limiting age-appropriate instrumental activities of daily living;
- CTCAE Grade 3: Severe or medically significant but not immediately life-threatening; hospitalization or prolongation of hospitalization indicated; disabling; limiting self-care activities of daily living;
- CTCAE Grade 4: Life-threatening consequences; urgent intervention indicated; or
- CTCAE Grade 5: Death related to the AE.

8.1.3.2 Causality assessment

The relationship of an AE to the administration of study drug is to be assessed according to the following definitions:

- **No (not related or unlikely related):** The time course between the administration of study drug and the occurrence or worsening of the AE rules out a causal relationship and/or another cause (concomitant drugs, therapies, complications, etc) is suspected; or
- **Yes (possibly, probably, or definitely related):** The time course between the administration of study drug and the occurrence or worsening of the AE is consistent with a causal relationship and no other cause (concomitant drugs, therapies, complications, etc) can be identified.

Note: The definition implies a reasonable possibility of a causal relationship between the event and the study drug. This means that there are facts (evidence) or arguments to suggest a causal relationship.

The following factors should also be considered:

- **The temporal sequence from study drug administration:** The event should occur after the study drug is given. The length of time from study drug exposure to event should be evaluated in the clinical context of the event;
- **Underlying, concomitant, intercurrent diseases:** Each report should be evaluated in the context of the natural history and course of the disease being treated and any other disease the patient may have;
- **Concomitant drug:** The other drugs the patient is taking or the treatment the patient receives should be examined to determine whether any of them might be recognized to cause the event in question;
- **Known response pattern for this class of study drug:** Clinical and/or preclinical data may indicate whether a particular response is likely to be a class effect;
- **Exposure to physical and/or mental stresses:** The exposure to stress might induce adverse changes in the recipient and provide a logical and better explanation for the event; and
- **The pharmacology and PK of the study drug:** The known pharmacologic properties (absorption, distribution, metabolism, and excretion) of the study drug should be considered.

8.1.4 Adverse Events of Special Interest

The Investigator will monitor each patient for clinical and laboratory evidence of predefined AESIs throughout the patient's participation in this study.

The Investigator will assess and record any additional information on the AESI in detail on an AE eCRF, which must be completed within 24 hours of awareness of the event, following the same procedure as for serious AEs (SAEs) (see [Section 8.3](#)).

For this study, CTCAE Grade ≥ 2 anemia, defined as hemoglobin < 10 g/dL, AND absolute reticulocyte counts of $< 50\%$ of the baseline value (Screening Study Visit 2), which are confirmed by repeat testing, will be considered an AESI.

During the course of the study, additional AESIs may be identified by the Sponsor. AESIs must be recorded in the eCRF.

8.2 Serious Adverse Events

An AE or adverse reaction is considered serious if, in the view of either the Investigator or Sponsor, it results in any of the following outcomes:

- Death;
- A life-threatening AE;

Note: An AE or adverse reaction is considered "life-threatening" if, in view of either the Investigator or Sponsor, its occurrence places the patient at immediate risk of death. It does not include an event that, had it occurred in a more severe form, might have caused death.

- Requires hospitalization or prolongation of existing hospitalization;

Note: Any hospital admission with at least 1 overnight stay will be considered an inpatient hospitalization. An emergency room or urgent care visit without hospital admission will not be recorded as a SAE under this criterion, nor will hospitalization for a procedure scheduled or planned before signing of informed consent/assent, or elective treatment of a pre-existing condition that did not worsen from baseline. However, unexpected complications and/or prolongation of hospitalization that occur during elective surgery should be recorded as AEs and assessed for seriousness. Admission to the hospital for social or situational reasons (ie, no place to stay, live too far away to come for hospital visits, respite care) will not be considered inpatient hospitalizations.

- A persistent or significant disability/incapacity or substantial disruption of the ability to conduct normal life functions;
- A congenital anomaly/birth defect; or
- An important medical event.

Note: Important medical events that do not meet any of the above criteria may be considered SAEs when, based upon appropriate medical judgment, they may jeopardize the patient and may require medical or surgical intervention to prevent one of the outcomes listed above. Examples of such medical events include allergic bronchospasm requiring intensive treatment in an emergency room or at home, blood dyscrasias or convulsions that do not result in inpatient hospitalizations, or the development of drug dependency.

8.3 Serious Adverse Event Reporting – Procedures for Investigators

8.3.1 Initial Reports

All SAEs occurring from the time of informed consent/assent until 30 days after the last study drug dose must be recorded in the electronic data capture (EDC) and be reported to the Calliditas Patient Safety Mailbox at [contact] within 24 hours of the knowledge of the occurrence. Following 30 days after the last study drug dose, any SAE that the Investigator considers related to study drug must be reported to the Calliditas Patient Safety Mailbox.

To report the SAE, complete the Safety Report Form along with supporting documents if applicable (eg, laboratory reports, hospital discharge summaries, etc) and report to the Calliditas Patient Safety Mailbox at [contact] or call the Calliditas SAE reporting line, and email the completed paper Safety Report Form to Calliditas (contact information listed below) within 24 hours of awareness.

The Investigator is obliged to respond to any request for follow-up information (eg, additional information, event outcome, final evaluation, or other records where needed) or to any question the Sponsor (or designee) may have concerning the SAE within the same timelines as those noted above for initial reports. This is necessary to ensure prompt assessment of the event by the Sponsor (or designee) and, as applicable, to allow the Sponsor to meet strict regulatory timelines associated with expedited reporting obligations for events of this nature.

Calliditas SAE reporting line:
Telephone (Germany): [name]
Email: [contact]

8.3.2 Follow-Up Reports

During the study (and after the patient's participation in the study has ended), all AEs and SAEs should be followed proactively by the Investigator until the event resolves or the condition stabilizes to a level acceptable to the Investigator, or until the patient is lost to follow-up.

At the time the patient study participation ends, all ongoing AEs and SAEs should be evaluated for resolution. New or updated information will be recorded in the originally completed eCRF and the Investigator will submit any updated SAE/AESI information to the Sponsor (or designee) within the same timelines and procedure as noted above for initial reports after receipt of the information.

8.4 Product Complaints

Product complaints will be collected if they occur in the study. A product complaint is any alleged deficiency related to the identity or quality of a study drug, after it is released for distribution to a site or to a patient. This includes all components distributed with the drug, such as packaging, drug containers, labelling, and inserts.

Examples include the following:

- Packaging that is damaged or broken;
- Missing or illegible labelling;
- Inability of customer to administer the product; and
- Product with an unexpected color, appearance (eg, broken tablets), or taste.

Product complaints should be reported by filling out the Product Complaint Report Form and emailing it to [contact].

Any AEs that are associated with a product complaint, including observed or volunteered problems, complaints, or symptoms, are to be recorded on the appropriate eCRF, per instructions for AE Reporting in [Section 8.3](#).

8.5 Pregnancy Reporting

If a patient becomes pregnant during the study, the Investigator is to stop dosing with study drug(s) immediately and the patient should be withdrawn from the study.

A pregnancy is not considered to be an AE or SAE; however, any pregnancy occurring during the study and up to 30 days after the last dose of study drug must be reported to the Calliditas Patient Safety Mailbox within 24 hours of knowledge of the event. The Calliditas Patient Safety Mailbox will then provide the Investigator/site the Pregnancy Form for completion. The Investigator/site must complete the Pregnancy Form and email it back to the Calliditas Patient Safety Mailbox at [contact].

If the female partner of a male patient becomes pregnant while the patient is receiving study drug, the Investigator should notify the Calliditas Patient Safety Mailbox as described above.

The pregnancy should be followed until the outcome of the pregnancy, whenever possible. Once the outcome of the pregnancy is known, the Pregnancy Form should be completed and emailed to the Calliditas Patient Safety Mailbox. If the outcome of the pregnancy meets the criteria for immediate classification as an SAE (ie, postpartum complication, spontaneous abortion, stillbirth, neonatal death, or congenital anomaly), the Investigator should follow the procedures for reporting an SAE.

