3.1.2 Study Duration

The start of the study will be the date on which the first patient provides informed consent/assent, and the end of the study will be the last patient's last assessment.

The estimated study duration for an individual patient is approximately 32 weeks. Following a 4-week Screening Period (Note: the Screening Period may be longer than 4 weeks, as needed, to complete genetic testing), patients will receive setanaxib or placebo for a 24-week Treatment Period, followed by a 4-week Follow-up Period.

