4 SELECTION AND WITHDRAWAL OF PATIENTS

4.1 Inclusion Criteria

Patients who meet all of the following criteria will be eligible to participate in the study:

1. Male or female patients aged 12 to 50 years, inclusive, at the time of informed consent/assent;
For sites in the EU: Male or female patients aged 18 to 50 years, inclusive, at the time of informed consent;
2. Diagnosis of Alport syndrome by genetic testing (documented mutation in a gene associated with Alport syndrome [ie, COL4A3, COL4A4, or COL4A5]). Patients with a variant of uncertain significance should not be included in the study;

Note: Genetic test results are to be available prior to initiating other Screening procedures. In cases where genetic testing results are not available but the patient is likely to fulfill the other inclusion and exclusion criteria and has provided consent/assent, a sample for genetic testing should be processed locally and the Screening Period duration can be prolonged with the time it takes to receive the genetic test results. All other Screening assessments must be completed within 4 weeks (± 7 days) prior to randomization.

3. Weight ≥ 40 kg;
4. Willing and able to give informed consent (and assent, where applicable), in accordance with local age requirements, and to comply with the requirements of the study;
5. Female patients of childbearing potential must use a highly effective method of contraception to prevent pregnancy for ≥ 4 weeks before randomization and must agree to continue strict contraception (as specified in 5c) up to 90 days after the last dose of IMP;
 - a. For the purposes of this study, women of childbearing potential (WOCBP) are defined as “fertile, following menarche and until becoming postmenopausal unless permanently sterile. Permanent sterilization methods include hysterectomy, bilateral salpingectomy, and bilateral oophorectomy”;
 - b. Postmenopausal state is defined as no menses for 12 months without an alternative medical cause. In female patients who are not using hormonal contraception or hormonal replacement therapy but with suspected menopause and less than 12 months of amenorrhea, a high follicle-stimulating hormone level in the postmenopausal range will be required at Screening to confirm a postmenopausal state; and
 - c. Highly effective contraception is defined as methods that can achieve a failure rate of less than 1% per year when used consistently and correctly. These methods include the following:

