 - Combined (estrogen and progestogen containing) hormonal contraception associated with inhibition of ovulation (oral, intravaginal, or transdermal);
 - Progestogen-only hormonal contraception associated with inhibition of ovulation (oral, injectable, or implantable);
 - Intrauterine device;
 - Intrauterine hormone-releasing system;

- Bilateral tubal occlusion;
 - Vasectomized partner; and
 - Sexual abstinence (refraining from heterosexual intercourse during the entire period of risk associated with the study treatments, ie, up to 90 days after the last dose of IMP). The reliability of sexual abstinence needs to be evaluated in relation to the duration of the clinical study and the preferred and usual lifestyle of the patient. Periodic abstinence (calendar, symptothermal, or post-ovulation methods), withdrawal (coitus interruptus), spermicides only, and lactational amenorrhea method are not acceptable methods of contraception.
6. Female patients of childbearing potential must have a negative serum pregnancy test at Screening and a negative urine pregnancy test at Visit 3 (after randomization and before dosing);
 7. Male patients with female partners of childbearing potential must be willing to use a condom and require their partner to use a highly effective contraceptive method (as defined in the list in [inclusion criterion 5c](#)). Female condom and male condom should not be used together. This requirement begins at the time of informed consent/assent and ends 90 days after receiving the last dose of IMP;
 8. Male patients must be willing not to donate sperm and female study patients must be willing not to donate eggs from baseline until 90 days after the last dose of IMP;
 9. $\text{eGFR} \geq 30 \text{ mL/min/1.73 m}^2$ at Study Visit 1 or 2, calculated at the central laboratory using the CKD-EPI formula for patients ≥ 18 years of age and the revised bedside Schwartz formula for patients 12 to 17 years of age;
 10. Proteinuria ($\text{UPCR} \geq 90 \text{ mg/mmol [0.8 g/g]}$) at 2 consecutive measurements (24-hour urine sampling), separated by at least 2 weeks and calculated by the central laboratory;
 11. Receiving maximum allowed dose or maximum-tolerated daily dose of an ACEi and/or ARB that has been stable for at least 8 weeks prior to consent/assent; and
- Note: A stable dose is defined as a dose within 25% of the dose at randomization.
- Note: Patients with proven intolerance to ACEi and ARB are allowed in the study.

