8.8 Clinical Laboratory Evaluations

Clinical laboratory evaluations (including serum chemistry, hematology, endocrinology, and urinalysis) will be collected at timepoints specified in [Appendix A](#).

Baseline values for liver tests (ALT, AST, and total bilirubin) are determined by averaging the values obtained at Screening Visits 1 and 2 to obtain the arithmetic mean.

For WOCBP only: a serum pregnancy test will be performed at Study Visit 2. A pregnancy test via a local urine assessment will be performed at all other applicable study visits prior to study drug dosing.

The total number of venipunctures and the total volume of blood collected during the study will be limited to that needed for PK, PD, and safety assessments. The total whole blood volume collected during the study will not exceed those allowed per European Medicines Agency guidance (Ethical considerations for clinical trials on medicinal products conducted with minors).

See [Appendix B](#) for the complete list of analytes.

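### Mandatory pregnancy reporting stops at 30 days after the last dose for patients and at the last dose for partners, while the protocol's own period of reproductive risk runs to 90 days

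*Protocol*

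**What the plan says.** Protocol Section 4.1 sets the preventive rules. Under criterion 5, women of childbearing potential must agree "to continue strict contraception (as specified in 5c) up to 90 days after the last dose of IMP". The abstinence item under criterion 5c gives the reason for the span: abstinence has to cover the "entire period of risk associated with the study treatments, ie, up to 90 days after the last dose of IMP". For men with female partners of childbearing potential, criterion 7 says: "This requirement begins at the time of informed consent/assent and ends 90 days after receiving the last dose of IMP". Criterion 8 bars sperm and egg donation until the same 90-day point.

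Protocol Section 8.5 sets the reporting rules. For patients, "any pregnancy occurring during the study and up to 30 days after the last dose of study drug must be reported" within 24 hours of the site learning of it. For partners, the sponsor's safety mailbox is to be notified "If the female partner of a male patient becomes pregnant while the patient is receiving study drug". A report leads to a Pregnancy Form and, where possible, follow-up to outcome; listed outcomes such as spontaneous abortion or congenital anomaly are then handled as SAEs. The pregnancy itself is not treated as an AE or SAE.

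Three other places bear on the point. Section 3.1.2 has 24 weeks of treatment "followed by a 4-week Follow-up Period". Section 8.8 says that "A pregnancy test via a local urine assessment will be performed at all other applicable study visits prior to study drug dosing", and Appendix A puts the last test at the Week 28 visit (±7 days). Section 8.3.1 requires all SAEs to be reported until 30 days after the last dose and, beyond that, only those the investigator considers related. The SAP does not deal with pregnancy reporting.

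**The concern.** One part of the protocol treats the 90 days after the last dose as a time when conception carries a treatment-related risk. Another part sets the duty to report a pregnancy and follow its outcome, and ends that duty at 30 days for patients and at the last dose for partners. A site that follows both rules exactly could learn of a conception on Day 60, inside the stated period of risk, and have no obligation to report it or to open a Pregnancy Form.

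What is at stake is the completeness of pregnancy-exposure information, not the trial's inference. This is the first study of setanaxib in Alport syndrome and the first in adolescents (Protocol Sections 1.6.1 and 1.6.2), and it enrols patients aged 12 to 50. Exposed pregnancies will be rare, so each one is informative.

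**Working it through.** The documents state no figure to reproduce. The check is a comparison of windows.

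**Inputs**
- Stated period of risk after the last dose: C = 90 days (Section 4.1, criteria 5, 5c and 7; criterion 8 for donation).
- Patient reporting: during the study and up to 30 days after the last dose (Section 8.5).
- Partner reporting: only while the patient is on drug, so 0 days after the last dose (Section 8.5).
- Last visit: Week 28, target Day 197 in the SAP visit table, ±7 days. The Week 24 morning dose is taken at the site, so for a completer the Week 24 visit is taken as the last dose.

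**Formula.** For a patient, days covered after the last dose = max(30, days from last dose to Visit 9), reading the study as that patient's own participation. Uncovered share = (C − days covered) / C, with a floor of 0.

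**Female patients who complete treatment**
- Visit 9 at 21 or 28 days after the last dose: max = 30, so (90 − 30)/90 = 60/90 = 66.7%.
- Visit 9 at 35 days: (90 − 35)/90 = 55/90 = 61.1%.
- Widest windows, Week 24 visit 7 days early and Week 28 visit 7 days late: 28 + 14 = 42 days, so (90 − 42)/90 = 48/90 = 53.3%.

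**Female patients who stop drug early but stay to Day 197**
- Last dose at Week 20 (Day 141): 197 − 141 = 56 days covered; 34/90 = 37.8%.
- Last dose at Week 18 (Day 127): 70 days covered; 20/90 = 22.2%.
- Last dose on or before Day 197 − 90 = Day 107 (about Week 15): 0%.

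**Partners of male patients**
- (90 − 0)/90 = 90/90 = 100%. Visit timing and continued follow-up do not change this, because the partner rule is tied to receiving drug.

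**Does another rule close the gap?**
- AE and SAE reporting does not capture the pregnancy, because Section 8.5 says a pregnancy is neither.
- Section 8.3.1 keeps related SAEs reportable after 30 days with no end date. A congenital anomaly (an SAE under Section 8.2) would qualify if the investigator heard of it and judged it related. But without a required pregnancy report, nothing starts the outcome follow-up through which the investigator would hear of it.
- No scheduled test or visit falls later than Week 28 plus 7 days.

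**How many pregnancies could be involved?** Take as an upper bound that all 20 patients (the maximum randomized, Section 4.3) are women of childbearing potential who complete treatment. At the 1% annual failure rate that criterion 5c uses as its ceiling, 20 × 0.01 × 60/365 = 0.03 pregnancies on Days 31 to 90. At an assumed 10% a year, 0.33. Actual numbers should be lower at either rate, because men and women not of childbearing potential are also enrolled; in addition, about one third of patients receive placebo and carry no drug exposure.

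**The case against.** The strongest reply is that the two windows do different jobs. Contraception rules are a preventive margin and reporting rules are an administrative duty, and no passage says they must match. Thirty days is also the limit used for SAE reporting, the primary estimand and treatment-emergent events. Protocol Section 1.4.1 gives single-dose half-lives of about 8 to 14 hours for setanaxib and 9 to 12 hours for the active metabolite; 30 days is 720 hours, and 720/14 is about 51 half-lives at the longest value. Section 1.3.2 reports no genotoxicity, no treatment-related malformations, unaffected sperm parameters, and no embryo-fetal toxicity apart from lower fetal weight at the top rat dose.

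Much of this stands as argument about which period is appropriate. It does not explain why the protocol itself calls 90 days the period of risk and then ends reporting earlier. The phrase appears only in the abstinence item, but criteria 5 and 7 run to the same day. Nor does it explain why, within Section 8.5, patients and partners have different end points.

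A reader might infer that Days 31 to 90 are simply unobserved, or that adverse pregnancy outcomes in that time would be lost. The documents do not support that. Related SAEs remain reportable without time limit, and a patient still in the study is covered for longer than 30 days. The accurate description is that the time lies outside mandatory pregnancy reporting.

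Two looser readings of Section 8.5 would narrow the gap. If the study means the whole trial, which ends with the last patient's last assessment, early enrollees are covered longer; but the explicit 30-day limit would then do little work. If the general sentence on any pregnancy includes partners, their gap falls to 60 of 90 days for a completer; but the separate partner sentence would then be redundant. That both readings are possible is itself a reason to clarify the section.

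**Conclusion.** The inconsistency is real and modest. Section 8.5 does not cover the period of risk that criterion 5c names. The part outside mandatory reporting is 60 of 90 days (67%) for a female patient who completes treatment with Visit 9 no later than 30 days after the last dose, 53% to 61% when Visit 9 falls 35 to 42 days after it, and down to 0% when drug stops by about Week 15 and follow-up continues. For partners it is 90 of 90 days.

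These are fractions of calendar time, not of risk, and the two-thirds figure should not be applied to everyone: it overstates the gap for some patients and understates it for partners. They rest on the patient-level reading of the study and on the partner sentence standing alone. Well under one pregnancy is expected in the uncovered patient window, even on the generous assumptions above. No endpoint, sample-size statement or planned analysis is touched.

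Nor do the documents show that 30 days is too short or 90 days too long. They show only that the two passages disagree.

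**What to change.** Reconcile Section 8.5 with criteria 5, 7 and 8, for patients and for partners, and resolve the unexplained patient/partner difference inside Section 8.5. The aim is that a pregnancy the site learns of within whatever the protocol states as its period of risk is reported and followed to outcome. The sponsor's safety team decides the period. The same edit should say whether the study in Section 8.5 means the patient's participation or the trial as a whole.

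The cost is an amended passage and matching safety-reporting instructions, with no added visits or tests. The limit of this change should be plain: it obliges reporting of what a site learns and does not add active detection after the last visit.
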